Visit ^a	1	2	3	4	5	6	7 2	8	9	10	11 2	12 2	13 2	14	15	16 2	17 2	18 ^b		19 ^d	
Day	-42/-35	-28	-20	-14	-7	1	7	14	21	28	35	42	48	56	64	71	78	84		86-88	
Collect CGM device and upload CGM data						Х												х	х		Upload CGM data to the site computer with QuintilesIMS Study Management Suite Software
Training: Glucometer, SMPG profiles, study diary		Х																			
Glucometer dispensation		Х																			
Fasting SMPG ^g		Х	Х	Х	Х	Х	Х	Х	Х	Х	Х	Х	Х	Х	Х	Х	Х	Х	Х	Х	Values of last 3 measurements before each visit must be recorded in eCRF
2hPPG							Х	Х	Х	Х	Х	Х	Х	Х	Х	Х	Х				Regularly as instructed by investigator
7-point SMPG						Х												Х	Х		
SMPG data upload to site's PC						Х								Х	Х			Х	Х	Х	Server independent from eCRF
Re-training: Glucometer, SMPG profiles, study diary		Х	Х			Х								Х	Х			Х			

	Screening (weeks)	I	Run-in	(week	s)		Intervention period (weeks)					Follow up	Notes								
Procedure	-6/-5	-4	-3	-2	-1		1	2	3	4	5	6	7	8	9	10	11	12	EOT ^C	2 to 4 days after last IMP dose	Visit Windows: Site visits: ±3 days Phone call visits: ±1 day relative to Visit 6
Visit ^a	1	2	3	4	5 2	6	7 2	8	9	10 2	11	12 2	13 2	14	15	16	17 2	18 ^b		19 ^d	
Day	-42/-35	-28	-20	-14	-7	1	7	14	21	28	35	42	48	56	64	71	78	84		86-88	
HbA1c, FPG	Х					х												Xh	х		Central lab h:In case of premature EOT, : HbA1c, FPG to be measured at Week 12
C-peptide	Х																				Central lab
Hematology, clinical chemistry	Х																				See Appendix 2, Section 10.2
Pregnancy test (WOCBP only)	Х					х												х			Serum pregnancy test for screening; urine pregnancy test for subsequent monitoring (if positive to be confirmed by a serum test).
AE/SAE	AE To be assessed and reported if any throughout the study																				
Hypoglycemia recording		To be assessed and reported if any throughout the study																			
DTSQs						Х												Х			
DTSQc																		Х			
MOS-sleep						Х												Х			

	Screening (weeks)	Run-in (weeks)								Ir	nterve	entio	n per	iod (v	veeks)				Follow up	Notes
Procedure	-6/-5	-4	-3	-2	-1		1	2	3	4	5	6	7	8	9	10	11	12	EOT ^C	2 to 4 days after last IMP dose	Visit Windows: Site visits: ±3 days Phone call visits: ±1 day relative to Visit 6
Visit ^a	1	2	3	4 2	5 2	6	7	8	9	10 2	11 2	12 2	13 2	14	15	16 2	17 2	18 ^b		19 ^d	
Day	-42/-35	-28	-20	-14	-7	1	7	14	21	28	35	42	48	56	64	71	78	84		86-88	
WPAI						Х												Х			

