9.2 SAMPLE SIZE DETERMINATION

The sample size calculation is based on the percent time spent in glucose range of \geq 70 to \leq 180 mg/dL (\geq 3.9 to \leq 10 mmol/L) at Week 12, assessed from CGM measurements obtained during Weeks 10, 11 and 12.

For this criterion of percent time in range, there is no predefined non-inferiority margin. A relative non-inferiority margin of 10% is considered.

Let m1 and m0 be the true means for the Toujeo and Tresiba groups, respectively.

The non-inferiority null hypothesis would be H0: $m1-m0 \le -0.1*m0$ or H0: $m1-0.9*m0 \le 0$ and the alternative hypothesis (H1): m1=m0.

Toujeo would be considered non-inferior to Tresiba if the lower limit of the 95% CI for the adjusted difference estimate of m1-0.9*m0 at Week 12 is >0.

To ensure 90% power, the sample size should satisfy:

$$1.96 - \frac{(0.1 * m0)}{\sqrt{\frac{1.81 * SD^2}{n}}} = -1.282$$

Where -1.282 is the 10th percentile of a standard normal distribution and SD the common SD.

Which leads to:

$$n = \frac{(1.96 + 1.282)^2 * 1.81 * SD^2}{(0.1 * m0)^2}$$

Assuming a common SD of 14.7%, an average percent time in range in the Tresiba treatment group of 56% (value from LPS14587), no true difference between both arms under H1, and a relative non-inferiority of 10%, a sample size of 131 evaluable patients per treatment group would provide at least 90% power to show non-inferiority of Toujeo with respect to Tresiba on the percentage of time plasma glucose within the range of \geq 70 to \leq 180 mg/dL at Week 12.

With the assumption of a non-evaluability rate of 22% 338 participants (169 per treatment arm) will have to be randomized.

Patient is evaluable for the primary endpoint if he/she as at least 10 days of useable CGM data (not necessarily consecutives) at Week 12 (see Section 8.1.1.2 for definition of useable data).

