1.3 DETERMINATION OF SAMPLE SIZE

The sample size calculation is based on the percent time spent in glucose range of \geq 70 to \leq 180 mg/dL (\geq 3.9 to \leq 10 mmol/L) at Week 12, assessed from CGM measurements obtained from Weeks 10 to 12.

For this criterion of percent time in range, there is no predefined non-inferiority margin. A relative non-inferiority margin of 10% is considered.

Let m1 and m0 be the true means for the Toujeo® and Tresiba® groups, respectively.

The non-inferiority null hypothesis would be H0: $m1-m0 \le -0.1*m0$ or H0: $m1-0.9*m0 \le 0$ and the alternative hypothesis would be H1: m1=m0.

Toujeo would be considered non-inferior to Tresiba if the lower limit of the 95% confidence interval (CI) for the adjusted difference estimate of m1-0.9*m0 at Week 12 is > 0.

To ensure 90% power, the sample size should satisfy:

$$1.96 - \frac{(0.1 * m0)}{\sqrt{\frac{1.81 * SD^2}{n}}} = -1.282$$

where -1.282 is the 10th percentile of a standard normal distribution and standard deviation (SD) the common SD, which leads to:

$$n = \frac{(1.96 + 1.282)^2 * 1.81 * SD^2}{(0.1 * m0)^2}$$

Assuming a common SD of 14.7%, an average percent time in range in the Tresiba treatment group of 56% (value from LPS14587), no true difference between both arms under H1, and a relative non-inferiority of 10%, a sample size of 131 evaluable patients per treatment group would provide at least 90% power to show non-inferiority of Toujeo with respect to Tresiba on the percentage of time plasma glucose within the range of \geq 70 to \leq 180 mg/dL at Week 12.

With the assumption of a non-evaluability rate of 22%, 338 patients (169 per treatment group) will be randomized.

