2.1.3 Efficacy endpoints

Observation period for efficacy endpoints

The 12–week randomized period for efficacy variables is defined as the time from randomization until Week 12 (Visit 18) for randomized patients, regardless of study treatment discontinuation.

CGM data

A patient is eligible for randomization if a minimum of 10 days (not necessarily consecutive) of useable CGM data are generated during 20 consecutive days at run-in period.

At Week 12, CGM is evaluable if there is at least 10 days of useable CGM data (not necessarily consecutives) within the analysis time windows (see Section 2.5.4) at Week 12 evaluation.

Useable CGM data for a day/a 24-hour CGM profile are defined as having:

- At least 80% time of records per 24 hours (ie, 231 data points among the 288 recorded in 24 hours).
- No gap (missing data) lasting for a total of ≥ 2 hours per 24 hours besides the warm-up time for the sensor after insertion.

For CGM endpoints, details on derivations are available in Section 2.5.

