Toujeo would be considered non-inferior to Tresiba if the lower limit of the 95% CI for the adjusted difference estimate of m1-0.9*m0 at Week 12 is > 0 (with m1=true means of Toujeo and m0=true means of Tresiba).

01-Jul-2021 Version number: 1

In addition to the non-inferiority testing that is the primary analysis, and only if non-inferiority of Toujeo in comparison to Tresiba on the percent time in the range of 70-180 mg/dL is demonstrated and if non-inferiority of Toujeo versus Tresiba on the glucose total CV is demonstrated (see Section 2.4.4.3 for multiplicity issues), superiority of Toujeo over Tresiba on the percent time in the range of 70-180 mg/dL will be tested.

The point estimate of difference in mean of percent time in range and the corresponding 95% CI will also be estimated using the following ESTIMATE statement in PROC GLM (in Step 2, See Section 2.5.3).

ESTIMATE "TOUJEO-TRESIBA" TREAT 1 -1

and the Step 3 will be done to obtain baseline-adjusted least-squares means estimates at Week 12 for both treatment groups as well as, the differences of these estimates, with their corresponding standard errors (SEs), 95% CI. The lower bound of the two-sided 95% CI for the adjusted difference estimate of m1 - m0 at Week 12 will be compared to 0 and subjected to a superiority test (if lower limit of 95% CI is >0).

The superiority comparison is considered as a secondary analysis of the primary efficacy variable.

Assumption assessment

The studentized residuals from the 1000 ANCOVA models described in Step 2 above with imputed data will be inspected and plotted against the predicted values, all in the same graph, for a visual assessment to detect any homoscedasticity.

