If no more than 2 out of the 6 questions comprising the total treatment satisfaction score are missing, the total treatment satisfaction score is imputed by calculating the average of the scores from the answered questions, dividing this sum by the number of answered questions and multiplying the average by six.

If items 2 or 3 are not answered, the frequency of hypoglycemia or hyperglycemia scores is considered as missing.

Handling of missing responses of WPAI

If the patient is employed, and Q2, Q4 Q5, and Q6 is missing then the scores will be imputed using average of all scores from other patients who answer the questions. Otherwise, only Q6 will be imputed using average of all scores from other patients.

Multiple imputation for primary analysis

Multiple imputation under MAR assumptions

Once the missing data pattern will be assessed, the programming process for this primary analysis will follow three steps (if monotone missing pattern is observed for all patients, then proceed directly with Step 1b):

• Step 1a: Use PROC MI to produce a monotone missing data pattern. A monotone Monte Carlo Markov Chain MCMC imputation model will be used to impute interim missing data. A sample SAS code for this imputation is shown below:

```
PROC MI NIMPUTE=1000 DATA=orig OUT=impute1 SEED=14947 MIN=0 MAX=100;
BY ARM;
MCMC IMPUTE=MONOTONE;
VAR BASE PTIR;
RUN;
```

• Step 1b: Use PROC MI to execute the second imputation using the data set produced in the first imputation. A sample SAS code for this imputation is shown below (if Step 1a was not done due to monotone missing, then NIMPUTE=1000 and DATA=ORIG, BY statement not needed):

```
PROC MI NIMPUTE=1 DATA=impute1 OUT=impute2 SEED=14947 MIN=0 MAX=100;
CLASS ARM HBACRIT1;
BY _IMPUTATION_;
MONOTONE METHOD=REG
VAR ARM HBACRIT1 BASE PTIR;
RUN;
```

• Step 2: Each of the 1000 imputed datasets will undergo an ANCOVA using fixed categorical effects of treatment group (Toujeo, Tresiba), randomization stratum of screening HbA1c (<8.0% versus ≥8.0%), and the baseline percent time in range value 1 using the following ESTIMATE statement in PROC GLM

```
PROC GLM DATA=impute2;
BY _IMPUTATION_;
CLASS ARM HBACRIT1;
MODEL PTIR = ARM HBACRIT1 BASE;
ESTIMATE "TOUJEO-0.9 TRESIBA" INTERCEPT 0.1 TREAT 1 -0.9;
RUN;
```

• Step 3: The 1000 analysis results will be combined using PROC MIANALYZE (Rubin's rule). A sample SAS code for this combined analysis is shown below:

```
PROC MIANALYZE PARMS=est;
MODELEFFECTS estimate;
RUN;
```

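### The primary multiple imputation uses only the ANCOVA covariates, so it is practically an available-case analysis; adding Week 12 HbA1c and FPG as auxiliaries is a cheap improvement

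*SAP*

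**What the plan says.** - **Imputation model.** SAP 2.5.3, Step 1b, lists "VAR ARM HBACRIT1 BASE PTIR": arm, HbA1c stratum, baseline TIR and Week 12 TIR. Step 1a uses baseline and Week 12 TIR by arm. It applies only to a non-monotone pattern, which SAP 2.4.4.1.1 does not expect. The code is labelled a sample, but the text names no other imputation variable.
- **Analysis model.** Step 2 regresses Week 12 TIR on arm, HbA1c stratum and baseline TIR.
- **When the endpoint is missing.** SAP 2.1.3: "At Week 12, CGM is evaluable if there is at least 10 days of useable CGM data". Protocol 9.2 plans for such losses: "With the assumption of a non-evaluability rate of 22" percent, 338 patients are to be randomized.
- **Other glycemic data at Week 12.** HbA1c and FPG are measured at Visit 18 (Protocol 8.1.2 and 8.1.3). The schedule of activities (Protocol 1.3) keeps them after premature end of treatment: "HbA1c, FPG to be measured at Week 12". A 7-point SMPG profile is due in the week before Visit 18 (Protocol 8.1.4).
- **Sensitivity analyses (SAP 2.4.4.1.2).** The per-protocol and COVID-19 analyses reuse the primary imputation. The missing-not-at-random (MNAR) analysis imputes treatment discontinuers by return to baseline and everyone else by the primary MAR method. SAP 2.3.1.2 keeps patients in the per-protocol set when CGM was performed as planned but is not evaluable.
- **Total CV.** SAP 2.4.4.2 applies a similar procedure to glucose total CV, the second step of the testing hierarchy.

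**The concern.** Multiple imputation can do two things that dropping patients cannot: bring in information from variables outside the analysis model, and make MAR more plausible by conditioning on more of what predicts both the outcome and its absence. With identical covariates in both models and only the outcome missing, it does neither to any useful degree.

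SAP 2.4.4.1.1 defines MAR as missingness that depends only on observed variables, but the model then conditions on three of them, all fixed before treatment. Glycemia during the study is measured and unused. The patients most affected are treatment completers whose CGM falls short of 10 useable days, because no planned sensitivity analysis treats them differently. At stake are some precision and the credibility of MAR for both endpoints in the hierarchy.

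**Working it through.** **Inputs from the documents (Protocol 9.2; SAP 1.3 and 2.4.4.1.1).** SD 14.7, control mean 56, true difference 0. On the margin: "A relative non-inferiority margin of 10% is considered", which is 0.1 × 56 = 5.6 points. Success requires that the "lower limit of the 95% CI for the adjusted difference estimate of m1-0.9*m0 at Week 12 is > 0". The variance factor is 1 + 0.9² = 1.81. Non-evaluability is 22%, with 169 randomized per arm.

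**1. The plan's own figure.** n = (1.96 + 1.282)² × 1.81 × 14.7² / 5.6² = 131.09, against 131 stated. Then 131.09 / 0.78 = 168.06, so 169 per arm and 338 in total, as stated. The expected evaluable number is 169 × 0.78 = 131.82 per arm, with 37.18 lost. Power at 131.82 is Φ(5.6 / √(1.81 × 14.7² / 131.82) − 1.96) = 90.2%.

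**2. What the planned imputation recovers.** Simulation: 169 per arm, 22% missing at random, 1,500 trials, 100 imputations each, residual SD 14.7.

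| Analysis | Mean SE of m1 − 0.9·m0 | Power |
|---|---|---|
| Full data | 1.523 | 95.9% |
| Available-case ANCOVA | 1.728 | 90.2% |
| Imputation as planned | 1.732 | 89.8% |
| Imputation plus one auxiliary, partial correlation 0.7 | 1.635 | 92.8% |

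The planned-imputation and available-case estimates correlate at 0.999. For m1 − m0 the equivalence is exact in the limit. For m1 − 0.9·m0, the baseline TIR of non-evaluable patients can add a negligible amount through the 0.1 × mean term; none was visible.

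**3. What auxiliaries could add.** With r² the share of residual Week 12 TIR variance that the auxiliaries explain, and n_aux the number of patients per arm who have them:

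effective n = 1 / [(1 − r²)/131.82 + r²/n_aux]

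n_aux is 169 if all non-evaluable patients have the auxiliaries and 131.82 + 0.5 × 37.18 = 150.41 if half do. Both r² and availability are assumptions, because the documents give neither.

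| Auxiliaries available in | r² | Effective n per arm | SE reduction | Power |
|---|---|---|---|---|
| – | 0 | 131.8 | – | 90.2% |
| all non-evaluable | 0.3 | 141.1 | 3.4% | 92.0% |
| all non-evaluable | 0.5 | 148.1 | 5.7% | 93.1% |
| half | 0.3 | 136.9 | 1.9% | 91.2% |
| half | 0.5 | 140.5 | 3.1% | 91.9% |

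First row worked, r² = 0.3: 1 / (0.7/131.82 + 0.3/169) = 141.1, and 1 − √(131.82/141.13) = 3.4%.

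**4. Dependence on the SD.** These powers take 14.7 as the residual SD. If it is the unadjusted SD and baseline TIR correlates 0.7 with Week 12 TIR (assumed), simulated power is already above 99% without auxiliaries and the power gain is under one point. The SE reduction remains: 1.236 to 1.165 for a partial correlation of 0.7.

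**5. Bias, as illustration only.** Suppose 22% are missing per arm and, in one arm only, the odds of missingness rise 1.5- to 2-fold per SD of worse auxiliary. With partial correlation 0.5 to 0.85 and residual SD 10.5 to 14.7, the planned imputation leaves about 0.5 to 1.8 points of bias in that arm's mean, against the 5.6-point margin. Including that auxiliary would address it.

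**The case against.** The strongest reply is that an imputation model matching the analysis model, backed by an MNAR sensitivity analysis, is a valid prespecified approach. That stands. Four further points bear on how far the concern reaches.

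- **Power.** A reader might infer that the trial is underpowered. It is not: the sample size was set on 131 evaluable patients per arm, so an imputation that recovers nothing still gives about 90%. Any gain is above target.
- **Discontinuation.** A reader might infer that treatment discontinuation is ignored. It is absent from the MAR model, but the MNAR analysis is built on it, and Protocol 7.1.1 asks for Week 10 to 12 CGM after discontinuation where possible. SAP 2.4.4.1.2 does not expect enough discontinuers with Week 12 CGM, so a discontinuation covariate would rest on those same few patients.
- **Partial CGM.** TIR from 1 to 9 useable days looks like the obvious auxiliary. Under SAP 2.1.3 and 2.5.1 the endpoint exists only with at least 10 useable days, so no patient has both quantities and a regression cannot estimate their relation. Redefined as TIR from all useable days, it equals the endpoint in every evaluable patient and would bypass the 10-day rule.
- **Strength and bias.** Neither strong prediction nor bias is shown. Evaluability depends on record completeness and gaps, not on glucose level, and the documents do not say what drives the 22%. The bias figures rest wholly on assumed one-arm missingness.

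What the reply does not remove is that completers with non-evaluable CGM receive the same three-covariate imputation wherever they are analyzed, while their Week 12 HbA1c and FPG go unused.

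**Conclusion.** The point holds as a cheap improvement. The planned imputation is, for practical purposes, an available-case ANCOVA, and its MAR assumption is conditioned on arm, stratum and baseline TIR only.

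The precision gain from auxiliaries is modest and assumed: for r² of 0.3 to 0.5, the SE is about 3% to 6% smaller if all non-evaluable patients have the auxiliaries and about 2% to 3% smaller if half do. The corresponding power is about 92% to 93% and 91% to 92%, against 90.2%, with 14.7 as residual SD. The lower availability deserves weight, because patients who withdraw or are lost to follow-up may have no Week 12 laboratory values. The better reason for the change is a more credible MAR assumption for completers with non-evaluable CGM. The documents do not support a claim that the primary result would be biased or the trial underpowered.

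**What to change.** In SAP 2.5.3, add Week 12 HbA1c and Week 12 FPG (values in the Day 77 to 91 window of SAP 2.5.4) to the imputation model for TIR, and do the same for glucose total CV. The mean of the Week 12 7-point SMPG profile is an optional third auxiliary. State that fully conditional specification or joint imputation is used where auxiliaries are themselves missing, since the pattern need no longer be monotone. Tabulate how many non-evaluable patients have each auxiliary, by arm.

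Keep the auxiliaries out of the ANCOVA: they are measured after randomization and belong only in the imputation. Leave out discontinuation status unless enough discontinuers have Week 12 CGM. Leave out partial-CGM TIR unless a day-level model is specified for it.

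The cost is SAP wording, slightly more complex code and a rule for missing auxiliaries. Data collection, estimand, margin and analysis model do not change.

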2.4.4.1 Analysis of primary efficacy endpoint(s)

2.4.4.1.1 Primary efficacy analysis

The primary efficacy endpoint is the percent time in glucose range is defined as the proportion of CGM readings falling into the range of \geq 70 to \leq 180 mg/dL [\geq 3.9 to \leq 10 mmol/L] at the Week 12 evaluation.

The primary efficacy endpoint will be analyzed using available data from the 12-week randomized period in ITT population via an analysis of covariance (ANCOVA) including the fixed categorical effects of treatment group (Toujeo versus Tresiba), randomization stratum of screening HbA1c (<8.0% versus \geq 8.0%), as well as, the continuous fixed covariate of baseline percent time in range value.

Multiple imputation (MI) assuming missing at random (MAR) will be used to replace missing data of percent time in glucose range at Week 12 and at baseline. The MAR assumption means that the missingness depends only on observed variables and not on the data that would have been observed (in the present case, the percent time in glucose range that would have been observed).

Moreover, the imputation procedure will also depend on the observed pattern of missingness:

- A) Monotone Pattern: Patients with missing baseline CGM and missing Week 12 CGM, or patients with baseline CGM but without a Week 12 value.
- B) Non-Monotone Pattern: Patients with missing baseline CGM but with a Week 12 CGM. Baseline CGM evaluable being used as a criterion to allow the randomization, this pattern is not expected to be represented in the study.

In order to explore missing data patterns for the primary efficacy analysis, number and percentage of patients in each of the following categories will be presented by treatment group.

- Pattern 1: patients with missing baseline CGM and missing Week 12 CGM,
- Pattern 2: patients with baseline CGM but missing Week 12 CGM,
- Pattern 3: patients with missing baseline CGM but with Week 12 CGM,
- Pattern 4: patients with baseline CGM and Week 12 CGM

Once missing data pattern will be assessed, the three-step programming process described in Section 2.5.3 will provide baseline-adjusted least-squares means estimates at Week 12 for both treatment groups, as well as, the differences of these estimates, with their corresponding standard errors (SEs), 95% CI, and one-sided P-values (H0: m1 - $0.9 \times m0 \le 0$, with m1 = true mean of Toujeo and m0 = true mean of Tresiba).

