2.4.4.1.3 Subgroup analyses

Where appropriate for the size of a subgroup (at least 30 patients in each category), exploratory analyses will be performed on the primary endpoint to summarize the treatment effects across subgroups defined by the following baseline and screening factors:

- Duration of diabetes (<10/>=10 years),
- Gender,
- Randomization strata of screening HbA1c categories (< 8.0% versus $\ge 8.0\%$),
- BMI (<30 and \geq 30 kg/m²).

Categories for subgroup analyses may be adapted according to data.

For each subgroup, the primary efficacy endpoint using available data from the 12-week randomized period in ITT population will be analyzed via an analysis of covariance (ANCOVA) including the fixed categorical effects of treatment group (Toujeo, Tresiba), randomization stratum of screening HbA1c (<8.0% versus $\geq 8.0\%$), the continuous fixed covariate of baseline percent time in range value, and adding the corresponding subgroup factor and subgroup factor-by-treatment interaction. LSmeans treatment difference (with the corresponding SEs and 95% CI) will be presented for each subgroup. The P-value for the interaction fixed term will be

obtained in order to evaluate whether the corresponding subgroup is behaving as a response modifier.

The ESTIMATE statement in PROC GLM, which reflects the subgroup analyses by baseline and screening factors, will be used. An example of SAS code for the subgroup analysis by gender is provided below:

Female group:

```
ESTIMATE "TOUJEO-TRESIBA" ARM 1 -1 SEX*ARM 1 0 -1 0;
```

Male group:

```
ESTIMATE "TOUJEO-TRESIBA" ARM 1 -1 SEX*ARM 0 1 0 -1;
```

Forest plot will be provided.

Further subgroup analyses may be performed if deemed necessary for the interpretation of results.

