In this SAS code above:

- orig: input dataset including one observation per patient in the ITT population
- BASE: Percentage of time in the glucose range of \geq 70 to \leq 180 mg/dL all time at baseline
- PTIR: Percentage of time in the glucose range of \geq 70 to \leq 180 mg/dL all time at Week 12

- ARM: treatment group as per randomized (TOUJEO/ TRESIBA)
- seed: the seed (14947) has been chosen arbitrarily and is based on the study code (LPS14947).
- HBACRIT1: randomization stratum of screening HbA1c (< 8.0% versus $\geq 8.0\%$)

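### The ESTIMATE statement prescribed for the primary non-inferiority test does not compute the baseline-adjusted m1 − 0.9·m0

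*SAP*

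**What the plan says.** SAP 2.4.4.1.1 defines the target correctly. The three-step process in 2.5.3 "will provide baseline-adjusted least-squares means estimates at Week 12 for both treatment groups", and Toujeo is non-inferior if the lower 95% limit for the adjusted m1 − 0.9·m0 is above 0.

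Step 2 in SAP 2.5.3 fits "MODEL PTIR = ARM HBACRIT1 BASE", with ARM and HBACRIT1 as class variables, "using the following ESTIMATE statement in PROC GLM". The contrast printed is "INTERCEPT 0.1 TREAT 1 -0.9". Steps 1a, 1b and 3 are each introduced as sample code; Step 2 is not.

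The variable list that follows has "ARM: treatment group as per randomized (TOUJEO/ TRESIBA" and no TREAT. It describes the covariate as "BASE: Percentage of time in the glucose range of" 70 to 180 mg/dL at baseline, that is, the raw percentage; nothing in the SAP centres it. The subgroup example in 2.4.4.1.3 uses ARM ("ESTIMATE 'TOUJEO-TRESIBA' ARM 1 -1 SEX*ARM 1 0 -1 0"), while the superiority statement in 2.4.4.1.1 again uses TREAT ("ESTIMATE 'TOUJEO-TRESIBA' TREAT 1 -1").

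**The concern.** There are two faults. The first is a naming slip: the statement refers to an effect that the model does not contain, so someone must edit it before it can run.

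The second is in the algebra. In an ordinary difference the arm weights are 1 and −1, and every other model term cancels. Here they are 1 and −0.9, so one tenth of the intercept, of the stratum effect and of the baseline term remains. The SAP carries the 0.1 for the intercept but not for HBACRIT1 or BASE. A programmer who corrects only the variable name gets either no estimate or an estimate of a different quantity.

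This line supplies the estimate, CI and p-value for the primary test. A wrong negative at Step 1 would also stop the total CV test and the superiority test (SAP 2.4.4.3). Repairing the primary contrast after unblinding would look data-driven.

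**Working it through.** **Plan's own figure.** SAP 1.3: n = (1.96 + 1.282)² × 1.81 × 14.7² / (0.1 × 56)² = 131.1, against 131 stated. Power at 131 is Φ(5.6/√(1.81 × 14.7²/131) − 1.96) = 90.0%. The planning figures are therefore sound for the contrast as defined in the prose.

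**What the contrast should be.** Write the Step 2 model as E(PTIR) = μ + α(arm) + γ(stratum) + β·BASE, and let B̄ be the mean baseline. Each LS mean is μ + α + ½(γ₁ + γ₂) + β·B̄. Hence

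LSmean(Toujeo) − 0.9·LSmean(Tresiba) = 0.1μ + α(Toujeo) − 0.9·α(Tresiba) + 0.05γ₁ + 0.05γ₂ + 0.1·B̄·β.

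**Estimability, with TREAT read as ARM.** In this design an estimable function must have its intercept weight equal to the sum of its arm weights and to the sum of its stratum weights. A numerical check on the over-parameterised design (L·X⁺X = L) gave:

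| Weights (intercept; arm; stratum; BASE) | Largest deviation | Result |
|---|---|---|
| 0.1; 1, −0.9; 0, 0; 0 | 0.0375 | not estimable |
| 0.1; 1, −0.9; 0.05, 0.05; 0 | about 5e-14 | estimable, at BASE = 0% |
| 0.1; 1, −0.9; 0.05, 0.05; 0.1·B̄ | about 5e-14 | the LS-mean contrast |
| 0; 1, −1; 0, 0; 0 (superiority) | about 5e-14 | estimable and correct |

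**Effect of the second row.** It falls short of the target by 0.1·β·B̄. With equal arms its expectation, which is the effective margin, is 0.1·(m0 − β·B̄).

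Inputs from the SAP: m0 = m1 = 56, SD 14.7, 131 per arm. Assumptions not in the documents: B̄ between 50 and 56, and SD 14.7 at both times, so that the slope equals the correlation and the residual SD is s = 14.7·√(1 − β²).

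- Correct contrast: SE = s·√(1.81/131); power = Φ(5.6/SE − 1.96).
- BASE = 0 contrast: SE = s·√(1.81/131 + (0.1·B̄)²/(262 × 14.7²)); power = Φ(margin/SE − 1.96).

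Example, B̄ = 50 and β = 0.3: s = 14.02. The correct SE is 1.648, and Φ(5.6/1.648 − 1.96) = 92.5%. With BASE = 0 the margin is 5.6 − 0.1 × 0.3 × 50 = 4.1, the SE is 1.674, and Φ(4.1/1.674 − 1.96) = 69%.

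| Slope | Effective margin, points (% of m0) | Power, BASE = 0 | Power, correct |
|---|---|---|---|
| 0 | 5.6 (10%) | 89% | 90% |
| 0.1 | 5.0–5.1 (9%) | 82–83% | 90% |
| 0.3 | 3.9–4.1 (7%) | 65–69% | 92.5% |
| 0.5 | 2.8–3.1 (5–5.5%) | 45–53% | 96% |
| 0.8 | 1.1–1.6 (2–3%) | 18–33% | over 99% |

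If the residual SD stays at 14.7 whatever the slope, power with BASE = 0 is 60–65% at slope 0.3 and 9–15% at slope 0.8, against 90%.

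**Simulation.** ANCOVA with 131 per arm, 3,000 runs, B̄ = 53, strata split 60/40 and a stratum effect of −4 points (all but the 131 assumed). At slopes 0.3, 0.6 and 0.8 the BASE = 0 contrast averaged 4.04, 2.46 and 1.39, while the correct one averaged 5.63–5.65. Non-inferiority was shown in 66%, 41% and 26% of runs, against 93%, 98% and 100%.

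**Type I error.** In a separate simulation (4,000 runs per scenario) at a true 10% deficit (m1 = 50.4), non-inferiority was wrongly declared in 2.6–2.9% of runs with the correct contrast (Monte Carlo error about 0.25 points), and in 0.0–0.2% with BASE = 0 at slopes 0.3–0.8.

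**The case against.** The strongest reply is that the printed line cannot itself cause the power loss. It names a variable outside the model, and with TREAT read as ARM and zero stratum weight it is not estimable. The loss belongs to a partial repair in which stratum weights appear and BASE stays at 0. Whether software would supply those weights is not settled by the documents, and SAS was not run. This stands: the power figures are conditional on that repair.

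It can also be said that the prose definition is clear and repeated in the protocol, that the code is an outline (Step 3 reads a dataset that no printed step creates), and that an estimate 1.5 to 4.5 points away from the value implied by the reported LS means would probably be noticed. These points reduce the chance of an undetected error. They do not remove the conflict: the prose sends the reader to Step 2, Step 2 is worded as a prescription, and no other section gives the missing weights.

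The error is conservative for a positive slope, and its size depends on a baseline mean, SD and slope that the documents do not give. The calculations also use 131 complete cases per arm, not the planned 169 per arm with multiple imputation. All of this is accepted.

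**Conclusion.** The concern holds and should be corrected before lock. With TREAT read as ARM, the Step 2 statement either gives no estimate or, once stratum weights are added, tests a stricter margin than the 10% specified. Neither is the estimand of SAP 2.4.4.1.1. That conclusion is algebraic and needs no outside assumption.

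The size does rest on assumptions. Over slopes of 0.3 to 0.8 and baseline means of 50 to 56, with the residual SD shrinking with the slope, the effective margin is about 2–7% of m0 and power is roughly 18–69%, against 92% or more for the correct contrast. At zero slope the margin is unchanged and power barely moves. With a positive slope the risk is a false failure of non-inferiority, not a false claim. The superiority statement has the naming slip only.

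**What to change.** Replace the Step 2 statement with

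`ESTIMATE 'TOUJEO-0.9 TRESIBA' INTERCEPT 0.1 ARM 1 -0.9 HBACRIT1 0.05 0.05 BASE <0.1 x mean of BASE>;`

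or centre BASE at that mean before Step 2, which makes a zero BASE weight correct. Then:

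- State that the strata are weighted equally, as in default LS means.
- State which mean of BASE is used. If no baseline value is missing, as SAP 2.4.4.1.1 expects, it is one fixed ITT mean. If any is imputed, say whether the mean is taken per imputed dataset or fixed.
- Require a programmed check that the result equals LSmean(Toujeo) − 0.9·LSmean(Tresiba).
- Use ARM instead of TREAT in the superiority statement.

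No code is printed for glucose total CV, so this is advice only: m1 − 1.1·m0 needs INTERCEPT −0.1, ARM 1 −1.1, HBACRIT1 −0.05 −0.05 and BASE −0.1 × its mean.

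The cost is a few words of SAP code before database lock, with no operational consequence.
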